2.3.2 Precautions Taken to Minimize Risks

In order to minimize the risk to subjects, all subjects will be monitored closely during their participation in this study. The study vaccines and GLA-AF have been produced according to current Good Manufacturing Practices (GMP) and will be administered by experienced investigators with drugs and equipment available for the treatment of anaphylaxis and other potential adverse reactions. All vaccine doses will be given by intramuscular injection to minimize injection site reactions such as pain. Furthermore, to reduce the likelihood of immediate-type allergic reactions to the vaccine formulations, all potential trial subjects will be screened for detectable IgE antibodies to *Na*-GST-1 and *Na*-APR-1 (M74); individuals with *Na*-GST-1 IgE antibodies detectable by the ELISA assay that are confirmed to be >0.35 kU_A/L by the ImmunoCAP method will be excluded from participation in the study, as will any individuals with *Na*-APR-1 (M74) IgE antibodies above the ELISA reactivity threshold.

Maintenance of Confidentiality

Participants will be asked to provide personal health information. All attempts will be made to keep this information confidential within the limits of the law. However, there is a chance that unauthorized persons will see the subjects' personal health information. All records will be kept in a locked file cabinet or maintained in a locked room at the study site. Electronic files will be password protected. Only people who are involved in the conduct, oversight, monitoring, or auditing of this study will be allowed access to the personal health information that is collected. Any publications from this study will not use information that will identify subjects by name.

2.3.3 Known Potential Benefits

Subjects may not receive any direct benefit from participation in this study. It is hoped that information gained in this study will contribute to the development of a safe and effective hookworm vaccine. All subjects will undergo a stool examination for ova and parasites at the Day 140 and Day 380 study visits. Subjects found to have a helminth infection at either of these study visits will be offered appropriate treatment at the conclusion of the study, free-of-charge. Free medical treatment will be provided to all vaccinated subjects during the active immunization phase and the follow-up period. If the investigators judge that a subject requires hospitalization, transportation will be arranged and the medical management of the subject will be monitored by a study physician and the local Independent Safety Monitor. Medical care for ailments not related to vaccination will not extend beyond the study period, but will be referred

to the nearest government-run health clinic. Medical care for ailments related to vaccination will extend at least until the condition has resolved or stabilized (if a chronic condition).

3 OBJECTIVES

3.1 Study Objectives

Primary:

Safety

1. To evaluate the safety and reactogenicity of three different dose concentrations of *Na*-APR-1 (M74) adjuvanted with Alhydrogel[®] or Alhydrogel[®] plus GLA-AF and administered either with or without *Na*-GST-1, in healthy Brazilian adults.

Secondary:

Immunogenicity

1. To assess the impact of co-administering *Na*-APR-1 (M74) and *Na*-GST-1 on antibody production by measuring the antibody levels to each antigen on study Day 126.

Tertiary:

Immunogenicity

1. To assess the impact of co-administration of *Na*-GST-1 on the duration of the antibody responses to *Na*-APR-1 (M74), and vice versa.
2. To assess the impact of co-administration of *Na*-GST-1 on the distribution of IgG subclass responses to *Na*-APR-1 (M74) and vice versa.
3. To assess the impact of co-administration of *Na*-GST-1 and *Na*-APR-1 (M74) on the functional capacity of vaccine-induced antibodies to neutralize the *in vitro* activity of the native enzymes (*Na*-GST-1 and wild type *Na*-APR-1).
4. To assess the impact of co-administration of *Na*-GST-1 and *Na*-APR-1 (M74) on the affinity of the antibody interactions with both recombinant antigens.
5. To assess the impact of co-administration of *Na*-GST-1 and *Na*-APR-1 (M74) on the production of memory B cells specific for each antigen.

Exploratory:

Immunogenicity

1. To assess the cellular immune responses to the *Na*-GST-1 and *Na*-APR-1 (M74) antigens following immunization.

3.2 Study Outcome Measures

3.2.1 Primary Outcome Measures

Safety

The following parameters will be evaluated for each dose and formulation of *Na*-APR-1 (M74) alone or co-administered with *Na*-GST-1:

1. Frequency of solicited injection site and systemic reactogenicity, graded by severity, on the day of each study vaccination through 14 days after each study vaccination.
2. Frequency of study vaccine-related serious adverse events from the time of the first study vaccination through approximately 9 months after the last study vaccination.
3. Frequency of clinical safety laboratory adverse events.
4. Frequency of unsolicited adverse events, graded by severity, from the time of each study vaccination through approximately 1 month after each study vaccination.
5. Frequency of new-onset chronic medical conditions through approximately 9 months after the third study vaccination.
6. Frequency of Adverse Events of Special Interest through approximately 9 months after the third study vaccination.

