3. To assess the impact of co-administration of *Na*-GST-1 and *Na*-APR-1 (M74) on the functional capacity of vaccine-induced antibodies to neutralize the *in vitro* activity of the native enzymes (*Na*-GST-1 and wild type *Na*-APR-1).
4. To assess the impact of co-administration of *Na*-GST-1 and *Na*-APR-1 (M74) on the affinity of the antibody interactions with both recombinant antigens.
5. To assess the impact of co-administration of *Na*-GST-1 and *Na*-APR-1 (M74) on the production of memory B cells specific for each antigen.

Description of Study Design:

Double blind, randomized, controlled, dose-escalation Phase 1 clinical trial in hookworm exposed adults living in the area of Americaninhas, Minas Gerais, Brazil. Subjects will receive three

doses of the assigned vaccine delivered intramuscularly on approximately Days 0, 56, and 112.

Safety will be measured from the time of each study vaccination (Day 0) through 14 days after each study vaccination by the occurrence of solicited injection site and systemic reactogenicity events.

Unsolicited non-serious adverse events (AEs) will be collected from the time of the first study vaccination through approximately 1 month after each study vaccination. New-onset chronic medical conditions and Serious Adverse Events (SAEs) will be collected from the time of the first study vaccination through approximately 9 months after the third study vaccination (final visit). Clinical laboratory evaluations for safety will be performed on venous blood collected approximately 14 days after each vaccination.

Immunogenicity testing will include IgG antibody responses to each vaccine antigen, by an indirect enzyme-linked immunosorbent assay (ELISA) and also by ImmunoCAP, on serum obtained prior to each study vaccination and at time points after each vaccination (see Appendix A); antibody affinity by Surface Plasmon Resonance; functional activity of vaccine-induced antibodies via *in vitro* enzyme neutralization assays; and, antigen-specific memory B cell responses.

Recruitment and enrollment into the study will occur on an ongoing basis, with each group being recruited and vaccinated in sequence.

60 subjects will be enrolled into 6 groups of 10:

The first 20 subjects will be entered into Groups 1 and 2 through open sequential enrollment.

- Group 1 double-blind IP allocation (n=10):

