9 ASSESSMENT OF SAFETY

9.1 Specification of Safety Parameters

Safety will be assessed by the frequency and severity of:

1. Study vaccine-related serious adverse events occurring from the time of the first study vaccination through approximately 12 months after the last study vaccination.
2. Solicited Adverse Events – reactogenicity events occurring on the day of each study vaccination through 14 days after each study vaccination:
 - a) Injection site reactions including erythema (redness), induration (hardness)/swelling, pain, and tenderness.
 - b) Systemic reactions including fever, feverishness (chills/shivering/sweating), fatigue (tiredness), malaise (general unwell feeling), myalgia (body aches/muscular pain exclusive of the injection site), arthralgia (joint pain exclusive of the injection site), headache, and nausea.
3. Clinical safety laboratory adverse events occurring from the time of each study vaccination through approximately 14 days after each set of vaccinations. Parameters to be evaluated include WBC, ANC, hemoglobin concentration, and platelet count; ALT; and, creatinine.
4. Unsolicited Adverse Events – non-serious adverse events occurring from the time of the each study vaccination through approximately 28 days after each vaccination.
5. New-onset chronic medical conditions occurring from the time of the first study vaccination through approximately 9 months after the last study vaccination.
6. Adverse Events of Special Interest occurring from the time of the first study vaccination through approximately 9 months after the last study vaccination.

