9.4 Type and Duration of Follow-up of Subjects after Adverse Events

AEs will be recorded if they start from the time of the first study vaccination (Day 0) up to 28 days after each dose of study product. AEs limited to new-onset chronic medical conditions will be followed through approximately 9 months after the third study vaccination (Day 380).

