- Line listings of clinical and laboratory AEs classified as immediate (within the first 60 minutes), systemic, and local will be displayed in tables stratified by dose cohort and formulation of Na-APR-1 (M74) and formulation (i.e., no GLA-AF or 5 µg GLA-AF).
- AEs will be summarized by severity and relationship to vaccine formulation by individuals and dose of Na-GST-1, Na-APR-1 (M74), and GLA-AF.
- The frequency of vaccine-related SAEs will be tallied as well as summarized by body system, by vaccine formulation and dose cohort.

Primary Outcome Measures:

The following summary parameters will be evaluated for each dose and formulation of Na-APR-1 (M74) alone or co-administered with Na-GST-1:

1. Frequency of solicited injection site and systemic reactogenicity, graded by severity, on the day of each study vaccination through 14 days after each study vaccination.
2. Frequency of study vaccine-related serious adverse events from the time of the first study vaccination through approximately 9 months after the last study vaccination.
3. Frequency of clinical safety laboratory adverse events.
4. Frequency of unsolicited adverse events, graded by severity, from the time of each study vaccination through approximately 1 month after each study vaccination.
5. Frequency of new-onset chronic medical conditions through approximately 9 months after the third study vaccination.
6. Frequency of Adverse Events of Special Interest through approximately 9 months after the third study vaccination.

Analysis Plan:

The proportion of participants with at least one injection site AE will be compared by Na-APR-1 (M74) vaccine formulation and dose cohort and co-administration status with Na-GST-1. We will test the null hypotheses that the type and number of adverse events is the same across all groups by Fisher's exact test.

Laboratory results (hematological and clinical chemistry) will be examined for trends over time and any clinically significant values for individuals will be reported.

Secondary Objective: To assess the impact of co-administering Na-APR-1 (M74) and Na-GST-1 on antibody production by measuring the antibody levels to each antigen on study Day 126.

Secondary Outcome Measures:

The following parameters will be evaluated for each dose and formulation of Na-APR-1 (M74) alone or co-administered with Na-GST-1:

1. The IgG level by an indirect enzyme-linked immunosorbent assay (ELISA) on approximately Day 126.

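### The SAE outcome counts only events judged vaccine-related, and no SAE count by arm regardless of attribution is planned

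*Protocol*

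**What the plan says.** **Collection.** The Protocol Summary (Description of Study Design) places no relatedness limit on SAEs: "New-onset chronic medical conditions and Serious Adverse Events (SAEs) will be collected from the time of the first study vaccination", continuing to the final visit about 9 months after the third dose. Section 9.2.3 defines an SAE irrespective of relationship to vaccine.

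**What is counted as an SAE outcome.** Section 3.2.1 item 2, repeated in Section 11.4, is "Frequency of study vaccine-related serious adverse events from the time of the first study vaccination", running to about 9 months after the last dose. Section 9.1 item 1 has the same related-only limit. The one SAE-specific summary in Section 11.4 says: "The frequency of vaccine-related SAEs will be tallied as well as summarized by body system".

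**What is counted as unsolicited.** Section 3.2.1 item 4, also repeated in Section 11.4, is "Frequency of unsolicited adverse events, graded by severity, from the time of each study vaccination through approximately 1 month after each study vaccination", with no restriction by seriousness. Section 9.1 item 4 defines the same category as "non-serious adverse events occurring from the time of the each study vaccination through approximately 28 days after each vaccination". The Protocol Summary also restricts unsolicited AEs to non-serious ones.

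**Other relevant text.** Section 11.4 plans a general AE table by relationship, severity, formulation, dose cohort and co-administration status. It neither names nor excludes SAEs. Under Section 5.3.2, Na-APR-1 dose and GLA-AF are open throughout, and investigators learn the Na-GST-1 or saline allocation after all subjects have had their Day 140 visit.

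**The concern.** Only one contrast in this trial is randomised: Na-GST-1 versus saline within each Group. Hypothesis 1 in Section 11.1 is comparative on safety for co-administration. A count of all SAEs by arm needs no causal judgement. A count of related SAEs depends on an assessment made after randomisation, and for part of follow-up that assessment is made by investigators who know the arm. As written, the plan contains only the second kind of SAE count.

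The sections also disagree on whether an unsolicited AE can be serious. That disagreement decides whether an SAE judged unrelated has any place in the outcome list shortly after a dose. At stake is a clear SAE comparison in the data that Sections 2.2.3 and 15.4 say will inform the decision on paediatric testing.

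**Working it through.** **Step 1: the passages side by side.**

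| Place | SAEs | Unsolicited AEs |
|---|---|---|
| Protocol Summary | all collected, to about 9 months after dose 3 | non-serious only |
| 3.2.1 and 11.4, items 2 and 4 | related only, to about 9 months | no limit by seriousness, about 1 month after each dose |
| 9.1, items 1 and 4 | related only, to about 12 months | non-serious only, about 28 days after each dose |
| 11.4, SAE tally | related only | not addressed |

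Take an SAE judged unlikely or not related. It is outside the SAE outcome in every row that defines one. Under Section 9.1 it is outside the unsolicited outcome too. It then reaches a primary outcome only if it also qualifies as a solicited reaction, a laboratory AE, a new-onset chronic condition or an AESI (Section 3.2.1 items 1, 3, 5 and 6).

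**Step 2: how much follow-up the wider wording covers.** Inputs are doses on Days 0, 56 and 112 (Section 2.2.2), follow-up to Day 380 (Section 4) and the 28-day window (Sections 9.1 and 9.4).

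- Windows: Days 0–28, 56–84 and 112–140, so 3 × 28 = 84 days; 84/380 = 22.1%.
- Not covered: 28 + 28 + 240 = 296 days; 296/380 = 77.9%.
- Counting both end days: 3 × 29 = 87 of 381, leaving 294 (77.2%).
- Section 9.4 says "AEs will be recorded if they start from the time of the first study vaccination (Day 0) up to 28 days after each dose". If that is read as continuous recording from Day 0 to Day 140, then 380 − 140 = 240 days (63.2%) are not covered.

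Under the Section 9.1 wording, none of the 380 days is covered for an SAE judged unrelated.

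**Step 3: how long attribution is unblinded to the randomised arm.** Unblinding follows the last subject's Day 140 visit. For that subject, at most 380 − 140 = 240 nominal days remain. With the stated 3-month enrolment period (taken as 90 days), about 240 − 90 = 150 remain for the first subject enrolled.

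**Step 4: illustration of size.** The protocol's only probability figures are in Section 11.2, from P(at least one event) = 1 − (1 − p)^n. For p = 10% and n = 20 this gives 87.84%, as stated, and all 15 cells of the table reproduce. The protocol gives no SAE rate, so the rates below are assumptions. If a share r of SAEs is judged related, outcome 2 sees the rate p × r. For n = 60:

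| Assumed all-cause SAE rate | Any SAE occurs | Outcome 2 shows one, r = 50% | r = 25% | r = 0 |
|---|---|---|---|---|
| 2% | 70.2% | 45.3% | 26.0% | 0% |
| 5% | 95.4% | 78.1% | 53.0% | 0% |
| 10% | 99.8% | 95.4% | 78.1% | 0% |

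As a constructed example by randomised arm, 3/30 versus 1/30 SAEs with none judged related would be tallied as 0/30 versus 0/30. Each zero has an upper 97.5% limit of 1 − 0.025^(1/30) = 11.6%.

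**The case against.** The strongest reply is that nothing is lost. Section 9.2.4 requires all SAEs to be reported whatever their relationship, and Appendix A schedules an SAE assessment at every visit from Day 0 to Day 380. Section 9.3.1 sends all SAEs to the sponsor and the pharmacovigilance contractor, and Section 9.3.3 sends those judged unrelated to the regulators at least annually. The general AE table in Section 11.4 covers all relationships by arm, and its layout may be left to the analysis plan. Section 11.2 states the primary objective in terms of vaccine-related events, so the restriction follows a stated aim. The trial is also small: 3/30 versus 1/30 has a two-sided Fisher p of about 0.61.

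Most of this stands, and it rules out three stronger readings that a reader might infer.

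- *SAEs judged unrelated go unrecorded or are hidden from oversight.* The collection and reporting text contradicts this. The 28-day limit in Section 9.4 concerns AEs generally and does not override SAE collection to the final visit.
- *An SAE judged unrelated is always in neither outcome.* Outcome 4 in Section 3.2.1 has no seriousness limit, so on that wording an early one is counted.
- *Knowledge of Na-APR-1 dose and GLA-AF biases the randomised comparison.* Those factors are assigned by open sequential enrolment and are the same for both arms within a Group. The relevant knowledge is the Na-GST-1 allocation, and it comes only after all Day 140 visits.

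What the reply does not answer is that case reporting is not a comparison by arm, and that the general table promises no split by seriousness. The related-only limit is also not a detail left open for later: the protocol fixes it as a primary outcome and as the SAE tally.

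**Conclusion.** The point holds at moderate severity; it is not a must-fix. The SAE outcome and the SAE-specific tally are related-only in every place that defines them, and no SAE count by arm regardless of attribution is planned. Whether an SAE judged unrelated falls outside the unsolicited outcome as well depends on which section governs: always under Section 9.1, and for about 78% of follow-up under Section 3.2.1 (63% if recording is continuous to Day 140). The SAE comparison of Na-GST-1 with saline therefore depends on attribution, which is blinded to arm until all subjects have completed Day 140 and unblinded afterwards.

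The day counts rest on nominal visit days. The detection probabilities and the 3/30 versus 1/30 example are illustrations on assumed rates. They show how attribution can change the tally, not that an imbalance would be missed in this trial.

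**What to change.** Reword outcome 2 in Section 3.2.1, Section 9.1 item 1, and the outcome list and tally in Section 11.4 to: *frequency of all SAEs regardless of relationship, with the vaccine-related subset, by Na-GST-1 versus saline and by dose and formulation, from first vaccination to the final visit*. State which of the five relationship grades in Section 9.2.1 make up the subset.

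Reconcile the non-serious limit in Section 9.1 item 4 and the Protocol Summary with outcome 4 in Sections 3.2.1 and 11.4. Either remove it, or keep it everywhere and say that SAEs are counted separately whatever their relationship. While those lines are open, reconcile the SAE period as well: about 9 months after the last dose in Section 3.2.1, about 12 months in Section 9.1.

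The cost is wording in a few places and one extra table row. The data are already collected and the sample size does not change.

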3.2.2 Secondary Outcome Measures

Immunogenicity

The following parameters will be evaluated for each dose and formulation of *Na*-APR-1 (M74) alone or co-administered with *Na*-GST-1:

1. The IgG level by an indirect enzyme-linked immunosorbent assay (ELISA) on approximately Day 126.
2. The IgG level by ImmunoCAP on approximately Day 126.

3.2.3 Tertiary Outcome Measures

Immunogenicity

The following parameters will be evaluated for each dose and formulation of *Na*-APR-1 (M74) alone or co-administered with *Na*-GST-1:

1. The IgG antibody response, by an indirect enzyme-linked immunosorbent assay (ELISA) at approximately 7, 14, and 28 days after each vaccination, and approximately 3, 6, and 9 months after the third dose.

2. The IgG antibody response, by ImmunoCAP at approximately 7, 14, and 28 days after each vaccination, and approximately 3, 6, and 9 months after the third dose.
3. The IgG subclass distribution (IgG1, IgG3, and IgG4) by plate based ImmunoCAP on approximately Day 126.
4. The IgG subclass distribution by plate based ImmunoCAP each day of vaccination, approximately 28 days later, and approximately 3 and 6 months after the final vaccination.
5. The functional capacity of vaccine-induced antibodies to neutralize the *in vitro* activity of the native enzymes.
6. The affinity of the antibody interactions with both recombinant antigens at approximately 7, 14, and 28 days after each vaccination, and 3, 6, and 9 months after the third dose.
7. The production of memory B cells specific for each antigen on days of vaccination, approximately 28 days following each vaccination, and 6 and 9 months after the third dose.

3.2.4 Exploratory Outcome Measures

The following parameter will be evaluated for each dose and formulation of *Na*-APR-1 (M74) alone or co-administered with *Na*-GST-1:

1. Cellular immune responses following vaccination.

4 STUDY DESIGN

The study will be conducted as a randomized, placebo-controlled, double-blind Phase 1 dose-escalating clinical trial in healthy adult volunteers living in the hookworm-endemic area of Americaninhas, Brazil.

Prior to beginning study-related activities, the consent and cooperation of local municipal government leaders and representative community members will be sought, after which volunteers will be invited to participate in the study. After providing written informed consent and passing the informed consent comprehension questionnaire, volunteers will undergo eligibility screening, including a complete medical history, physical examination, hematology testing, serum glucose testing, liver and renal function testing, HIV antibody testing, Hepatitis B and C serology, and urinalysis; urine pregnancy testing will be performed on all female volunteers. In addition, all volunteers will be tested for serum IgE antibodies to *Na*-APR-1 (M74) and *Na*-GST-1, and a fecal examination will be performed for ova and parasites. All clinically significant abnormalities will be reviewed with volunteers and referral for follow-up care will be provided. After screening, those volunteers determined to be eligible, based on the inclusion and exclusion criteria, will be invited to participate in the study.

Sixty volunteers will be progressively enrolled into 1 of 6 Groups over a projected 3-month enrollment period, with each subject followed for 13 months post-enrollment (to Study Day 380). Group enrollment will be done in an open sequential fashion, whereas within each Group, investigational product (IP) assignment and vaccination will be done in a randomized double-blind fashion.

The first 20 subjects will be entered into Groups 1 and 2

- Group 1 double-blind IP assignment (n=10):
 - 5 subjects will receive 10µg *Na*-APR-1 (M74) delivered by IM injection in the deltoid muscle, with sterile saline administered to the alternate arm.
 - 5 subjects will receive 10µg *Na*-APR-1 (M74) delivered by IM injection in the deltoid muscle, with 100µg *Na*-GST-1 administered to the alternate arm.
- Group 2 double-blind IP assignment (n=10):
 - 5 subjects will receive 10µg *Na*-APR-1 (M74) plus 5µg GLA-AF delivered by IM injection in the deltoid muscle, with sterile saline administered to the alternate arm.
 - 5 subjects will receive 10µg *Na*-APR-1 (M74) plus 5µg GLA-AF delivered by IM injection in the deltoid muscle, with 100µg *Na*-GST-1 administered to the alternate arm.

The next 20 subjects will be entered into Groups 3 and 4

- Group 3 double-blind IP assignment (n=10):
 - 5 subjects will receive 30µg *Na*-APR-1 (M74) delivered by IM injection in the deltoid muscle, with sterile saline administered to the alternate arm.
 - 5 subjects will receive 30µg *Na*-APR-1 (M74) delivered by IM injection in the deltoid muscle, with 100µg *Na*-GST-1 administered to the alternate arm.

-
- Group 4 double-blind IP allocation (n=10):
 - 5 subjects will receive 30µg *Na*-APR-1 (M74) plus 5µg GLA-AF delivered by IM injection in the deltoid muscle, with sterile saline administered to the alternate arm.
 - 5 subjects will receive 30µg *Na*-APR-1 (M74) plus 5µg GLA-AF delivered by IM injection in the deltoid muscle, with 100µg *Na*-GST-1 administered to the alternate arm.

The final 20 subjects will be entered into Groups 5 and 6

- Group 5 double-blind IP allocation (n=10):
 - 5 subjects will receive 100µg *Na*-APR-1 (M74) delivered by IM injection in the deltoid muscle, with sterile saline administered to the alternate arm.
 - 5 subjects will receive 100µg *Na*-APR-1 (M74) delivered by IM injection in the deltoid muscle, with 100µg *Na*-GST-1 administered to the alternate arm.
- Group 6 double-blind IP allocation (n=10):
 - 5 subjects will receive 100µg *Na*-APR-1 (M74) plus 5µg GLA-AF delivered by IM injection in the deltoid muscle, with sterile saline administered to the alternate arm.
 - 5 subjects will receive 100µg *Na*-APR-1 (M74) plus 5µg GLA-AF delivered by IM injection in the deltoid muscle, with 100µg *Na*-GST-1 administered to the alternate arm.

As with other aluminum hydroxide-adsorbed vaccines, hypersensitivity reactions would be expected to occur within the first 24 hours after receipt of either of the two vaccines, and other severe local or systemic reactions within 72 hours of vaccination. Subjects will therefore be observed for immediate reactions following each vaccination for at least 1 hour, and will have a clinical assessment either in their home or at the study clinic on Days 1, 3, 7, and 14 following each vaccination. See **Appendix A** for the schedule of clinical and laboratory evaluations.

In order to review safety data at each dose of *Na*-APR-1 (M74)/Alhydrogel[®] prior to testing it in combination with the point-of injection addition of GLA-AF, and to review safety data at each dose of *Na*-APR-1 (M74)/Alhydrogel[®] prior to dose escalation, Groups will be enrolled and vaccinated in a staggered fashion. Conference calls between the investigators and the Safety Monitoring Committee (SMC) will be scheduled within the week prior to beginning vaccinations in Groups 3 and 5. A cumulative safety report will be submitted to the SMC before beginning vaccinations in these Groups that will include safety data from at least the first 14 days after vaccination of all subjects in the preceding Group. Written approval (via fax or email) to proceed to vaccinations of Groups 3 and 5 must be obtained from the SMC.

The SMC and Independent Safety Monitor will have access to the randomization code for the study, as they may wish to review the data in an unblinded fashion should significant safety questions arise prior to the final unblinding. The trial will not proceed to the next dose Group if any of the stopping criteria listed in **Section 9.5** are met or, in the clinical judgment of the SMC, Independent Safety Monitor, and/or DMID Medical Monitor the next higher dose would pose an unacceptable safety risk to the subjects.

